10.2 Study Variables

10.2.1 Efficacy Variables

10.2.1.1 Primary Efficacy Variable

The primary efficacy variable is the change from Baseline to Week 16 on the CDR Computerized Cognition Battery Continuity of Attention.

10.2.1.2 Key Secondary Efficacy Variable

The key secondary efficacy endpoint is the change from Baseline to Week 16 on the CDR Quality of Episodic Memory.

10.2.1.3 Other Efficacy Variables

The other secondary efficacy endpoints are the change from Baseline to Week 16 on the following measures:

1. ADCS-CGIC.
2. ADAS-cog (total score).
3. CDR Power of Attention.
4. CDR Speed of Memory Retrieval.
5. PDAQ.
6. SCOPA-SLEEP.
7. SAPS-PD.
8. NPI.
9. MoCA.

10.2.2 Exploratory Efficacy Variables

Exploratory efficacy endpoints include the change from Baseline to Week 16 on the individual component tasks of the CDR:

1. Word Presentation.
2. Immediate Word Recall.
3. Picture Presentation.
4. Simple Reaction Time.
5. Digit Vigilance.
6. Choice Reaction Time.
7. Numeric Working Memory.
8. Spatial Working Memory.
9. Delayed Word Recall.
10. Word Recognition.
11. Picture Recognition.

10.2.3 Pharmacokinetic Variables

- SYN120 plasma concentrations [REDACTED] and time point of IMP intake and blood sampling.

10.2.4 Safety Variables

Safety variables include the following:

- AEs.

Change from Baseline in:

- Vital sign parameters (pulse rate, systolic and diastolic BP).
- Change in body weight.
- Change from supine to standing BP (systolic and diastolic).
- UPDRS.
- C-SSRS.
- Standard 12-lead ECG (RR, PR, QRS, QT, and QT intervals corrected for heart rate using Fridericia's formula [QTcF]).
- Laboratory parameters: hematology, chemistry, and urinalysis.

10.3 General Statistical Considerations

Descriptive statistics will be displayed to provide an overview of the study results. For categorical variables, the number and percentage of patients in each category will be presented. The denominator for percentages will be based on the number of patients appropriate for the purpose of analysis. For continuous variables, descriptive statistics will include number of patients (n), mean, standard deviation (SD), median, minimum, and maximum.

In general, Baseline values for efficacy and safety variables will be determined from the last non-missing data collected prior to the first dose of study medication.

10.4 Planned Efficacy Analyses

10.4.1 Analysis of the Primary Efficacy Variable

The primary analysis will be performed on the mITT analysis set and will use a shared-baseline repeated measures analysis of variance (ANOVA) that includes fixed effects for visit (3 levels: baseline, Week 8, and Week 16) and the interaction between treatment group (2 levels: SYN120 and placebo) and post-baseline visit (2 levels), random center-specific intercepts, and unstructured within-person covariance. The repeated measures model yields estimates that are unbiased as long as loss to follow up and missing assessments are predictable from observed scores. Use of a shared baseline (i.e., no treatment main effect) reflects the true state of the population sampled prior to randomization and has the advantage of adjusting for any chance differences at baseline in a manner similar to analysis of covariance (ANCOVA) ([Liang and Zeger, 2000](#)) with potentially greater efficiency with more than one follow up visit and drop-out.

Treatment-dependent differences in the change from Baseline to Week 16 on the CDR Computerized Cognition Battery Continuity of Attention will be estimated by linear contrasts and tested using a two-tailed Wald-test at alpha = 0.05. A significant mean improvement over 16 weeks in CDR Continuity of Attention among participants randomized to SYN120 relative to mean changes among participants randomized to placebo would be considered evidence of therapeutic benefit from SYN120. As a sensitivity analysis if SYN120 is not found to be beneficial in the mITT sample, the same model will be applied to the PP sample and a nonparametric van Elteren test will be used to compare 16-week change scores in the PP sample, stratifying by center.

10.4.2 Key Secondary Efficacy Analyses

The key secondary efficacy variable will be analyzed in the mITT sample using the model specified for the primary analysis of the primary efficacy variable. Treatment-dependent differences in the change from Baseline to Week 16 on the CDR Quality of Episodic Memory will be estimated by linear contrasts and tested using a two-tailed Wald-test at alpha = 0.05. Equivalent sensitivity analyses as are planned for the primary efficacy variable will be applied to the key secondary efficacy variable.

10.4.3 Multiplicity Adjustment for Primary and Key Secondary Endpoints

If the effect of SYN120 on the primary outcome in the mITT sample is significant at alpha = 0.05, then testing the key secondary outcome at alpha = 0.05 maintains an overall type I error rate at 5% under a closed testing sequential analysis. When the primary analysis is not significant, we limit the overall type I error rate to 10% or less (depending on the magnitude of correlation between the primary and key secondary outcomes) when significance of the key secondary outcome alone is accepted as evidence of a therapeutic benefit from SYN120.

10.4.4 Other Efficacy Analyses

All continuous other (non-key) secondary and exploratory efficacy variables that are approximately normally distributed or can be made so by simple transformation will be analyzed using the model defined in the primary efficacy analysis ([Section 10.4.1](#)) using the mITT sample in a first round of testing. Outcomes that are not normally distributed will be transformed or compared between the treatment groups using a van Elteren test that incorporates stratification by center. Comparisons will be tested at two-tailed alpha = 0.05, recognizing that the totality of results will be evaluated in judging the potential of SYN120 as a therapeutic agent for PDD. If not significant in the mITT sample, additional sensitivity analyses of the other (non-key) secondary efficacy variables will use the PP sample.

10.5 Planned Safety and Other Analyses

10.5.1 Safety Analyses

Safety data, including AEs, vital signs, UPDRS, ECGs, physical examination, and clinical laboratory test results will be summarized descriptively for each treatment group. The frequency and type of any observed suicidal ideation will be described. Descriptive statistics of continuous measures will be provided for the observed data and for the change from Baseline at each measured time point. Adverse events will be summaries by dose group as counts of events and as the proportion of patients experiencing any given type of AE as classified by MedDRA system organ class and preferred term. Overall rates of AEs will be compared between treatments by negative binomial regression. Proportions of participants experiencing a given type of event will be compared between treatments by Fisher's exact test.

Laboratory test results will be classified as below the lower limit of normal, within normal limits and above the ULN. Shift tables will be used to summarize changes from Baseline to each visit by treatment group. Clinically significant physical or neurological exam findings and any clinically significant out-of-range laboratory tests are recorded as adverse events and will be documented in the AE summaries.

Analyses will be performed for the SS as treated.

10.5.2 Other Analyses

Patient Disposition

The number of patients who were screened, randomized, completed scheduled follow up, and prematurely withdrew study participation will be summarized overall and by treatment group. Reasons for non-participation and for withdrawal from study will also be presented.

Exposure to IMP/Compliance

The number of days of exposure to IMP will be summarized by treatment group. Compliance with IMP will be calculated as the number of doses taken divided by the scheduled number of doses taken, expressed as a percentage. Compliance will be summarized overall and by week for each treatment group. Time to discontinuation of IMP will be estimated using Kaplan-Meier product-limit estimates. Treatment-dependent differences will be tested by log-rank test.

Prior and Concomitant Medication Use

All prior and concomitant medications taken during the study period will be listed for each patient, including dosage and indication. Each medication will be coded using the World Health Organization (WHO) Drug Dictionary Enhanced and classified as a past medication (last dose taken prior to the first dose of IMP), a concomitant medication ongoing at Baseline, or a

concomitant medication initiated after Baseline. The percentage of patients taking each medication (or class of medications) will be summarized overall and by treatment group.

Pharmacokinetic Samples

Results of the plasma assays of SYN120 will be descriptively analyzed and reported in the clinical study report. Separate population analysis on the data from this study alone or combined with data from other studies as deemed appropriate will be performed and reported separately.

Optional Pharmacogenetic Substudy Data Analysis

The exploratory pharmacogenetic analyses are designed to investigate the association between genetic factors (genotypes) and the prediction of treatment response or intolerance. The pharmacogenetic analyses are not intended to be used for regulatory judgments pertaining to the safety or efficacy of the investigational drug. However, these data may be considered for voluntary submission, consistent with applicable regulatory guidance on this topic, in order to develop the knowledge base necessary to establish the validity of genomic biomarkers.

Pharmacogenetic data will be analyzed to describe frequencies of pre-specified polymorphisms related to 5HT6 and 5HT2a receptors, [REDACTED] Parkinson's disease, and cognition. Exploratory analyses of association between specific genetic polymorphisms and treatment response will be performed by adding genotype, genotype × visit, and genotype × treatment × visit terms to models for primary and secondary efficacy outcomes. Exploratory analyses of association between specific genetic polymorphisms and treatment intolerance will be performed in logistic regression models with drug discontinuation or occurrence of specific adverse events as outcomes and genotype, treatment, and genotype × treatment interaction as predictors.

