## 2. STUDY DESIGN

### 2.1. Overview

This is a multicenter, double-blind, placebo-controlled, two-arm, parallel-group, phase 2a randomized controlled trial to evaluate the safety, tolerability, and preliminary efficacy of a 16-week course of 100 mg QD SYN120 in men or women with a diagnosis of Parkinson's disease dementia (PDD) who are taking a cholinesterase inhibitor. Trial participation includes a screening visit, randomization to SYN120 or placebo, 16 weeks of follow-up on study drug, and a final safety visit 2 weeks after last dose of study drug. The trial is registered at Clinicaltrials.gov as study NCT02258152 (see <https://clinicaltrials.gov/ct2/show/NCT02258152>). Participants may also separately consent to DNA testing for a pharmacogenetics substudy. The aims and planned analyses of the pharmacogenetics substudy are not described here.

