## 3.8. Efficacy Analysis

### 3.8.1. Primary Analysis of the Primary Efficacy Endpoint

The primary efficacy analysis will be performed on the mITT sample using the adjudicated CDR data and will use a shared-baseline, repeated-measures analysis of variance that includes fixed effects for visit (3 levels: Baseline, Week 8, and Week 16) and the interaction between treatment group (2 levels: SYN120 and placebo) and post-baseline visit (2 levels: Weeks 8 and 16), random center-specific intercepts, and unstructured within-person covariance. The interaction between treatment group and visit will be restricted to post-baseline visits by including a numeric indicator variable (0 pre-treatment, 1 post-treatment) in the interaction. Use of a shared baseline reflects the true state of the population sampled prior to randomization and has the advantage of adjusting for any chance differences at baseline in a manner similar to analysis of covariance ([Liang and Zeger, 2000](#)) with potentially greater efficiency with more than one follow-up visit and drop-out. Data from Early Termination visits will be assigned to the next scheduled post-baseline visit. The following SAS code specifies the model:

```
proc mixed data=xxx method=reml;
  class site id trtrnd visit;
  model Value = visit post*trtrnd*visit;
  random intercept / subject=site type=vc;
  repeated visit / subject=id(site) type=un;
```

Treatment-dependent differences in the change from baseline to the week 16 visit on the CDR COA will be estimated by a linear contrast and tested using a two-tailed Wald-test at alpha = 0.05. The following SAS code specifies the linear contrasts used to estimate treatment- and visit-specific means, treatment- and visit-specific changes from baseline, and treatment-dependent visit-specific changes from baseline (with the sort order for treatment group being SYN120 first and placebo second):

```
estimate "0|Active |Wk  00" intercept 1 visit  1 0 0 post*trtrnd*visit 0 0 0  0 0 0 / cl;
estimate "0|Active |Wk  08" intercept 1 visit  0 1 0 post*trtrnd*visit 0 1 0  0 0 0 / cl;
estimate "0|Active |Wk  16" intercept 1 visit  0 0 1 post*trtrnd*visit 0 0 1  0 0 0 / cl;
estimate "1|Active |dWk 08" intercept 0 visit -1 1 0 post*trtrnd*visit 0 1 0  0 0 0 / cl;
estimate "1|Active |dWk 16" intercept 0 visit -1 0 1 post*trtrnd*visit 0 0 1  0 0 0 / cl;
estimate "0|Placebo|Wk  00" intercept 1 visit  1 0 0 post*trtrnd*visit 0 0 0  0 0 0 / cl;

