### 3.8.4. Subgroup Analyses

Differences in treatment efficacy will be explored in several pre-defined subgroups: site, age (median split), screening MoCA total score (median split), baseline LEDD (median split), and baseline cholinesterase inhibitor (donepezil vs. rivastigmine). Subgroup specific estimates will be obtained by including subgroup, subgroup  $\times$  visit, and subgroup  $\times$  treatment  $\times$  post-baseline visit terms to models for primary and key secondary efficacy outcomes based on the mITT sample.

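### The pharmacogenetic response model omits the post-baseline restriction on its genotype × treatment × visit term, which, read literally, costs precision for no gain

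*Protocol*

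**What the plan says.** Protocol 10.4.1 defines the base model. It has "fixed effects for visit (3 levels: baseline, Week 8, and Week 16"), and treatment enters only through its interaction with the two post-baseline visits. The reason given is: "Use of a shared baseline (i.e., no treatment main effect) reflects the true state of the population sampled prior to randomization". SAP 3.8.1 turns this into code: "The interaction between treatment group and visit will be restricted to post-baseline visits by including a numeric indicator variable (0 pre-treatment, 1 post-treatment").

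SAP 3.8.4 builds the subgroup models in the same spirit, with a subgroup term, its interaction with visit, and a three-way term with treatment. There the qualifier is written out; the last part of the sentence adds "post-baseline visit terms to models for primary and key secondary efficacy outcomes based on the mITT sample".

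Protocol 10.5.2 has the parallel structure with genotype in place of subgroup, but its three-way term names visit without the qualifier: the analyses "will be performed by adding genotype, genotype × visit, and genotype × treatment × visit terms to models for primary and secondary efficacy outcomes". The SAP does not settle the matter, because its section 2.1 says: "The aims and planned analyses of the pharmacogenetics substudy are not described here". Protocol 10.5.2 also limits the role of these analyses: "The pharmacogenetic analyses are not intended to be used for regulatory judgments pertaining to the safety or efficacy of the investigational drug".

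**The concern.** In the protocol's own vocabulary, visit includes baseline and the treatment interaction does not. A three-way term over all levels of visit carries its own treatment difference at baseline in each genotype. Adding it to a model that restricts treatment elsewhere does not preserve the restriction. Genotype is fixed before randomization, so within each genotype the true baseline difference between arms is zero. Estimating it spends information on a known quantity.

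What is at stake is the precision of the genotype-by-treatment contrast at Week 16, the quantity the substudy is meant to estimate (Protocol 7.13). It comes from at most 80 patients split by arm and genotype, fewer if some decline the optional sample, so it is imprecise to begin with.

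**Working it through.** **The plan's own figure.** The documents give no variance or power figure for the pharmacogenetic model. The only related figure is the main trial's power (Protocol 10.8, SAP 3.4): 80 randomized, 15% loss, effect size 0.69, two-sided 5% level. With 40 × 0.85 = 34 per arm, the two-sample t-test has power 0.800 (0.812 by the normal approximation). The stated figure of at least 80% is reproduced, and this point does not touch it.

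**Inputs for the pharmacogenetic contrast**
- Visits (baseline, Week 8, Week 16) and the restriction on treatment: Protocol 10.4.1, SAP 3.8.1.
- Baseline to Week 16 correlation r: not given; assumed 0.3 to 0.9.
- Genotype coding (class factor or numeric): not given; both tried.
- Genotype frequencies: not given; 50/50, 70/30, 49/42/9 and 25/50/25 tried.
- Dropout: 0%, or 15% after Week 8, using the ceiling in Protocol 10.8.
- Simplifications: equal variance at each visit, one common correlation, covariance treated as known, no site effect.

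**Closed form (class-coded genotype, complete data).** The contrast is the difference between two genotypes in the treatment effect on change from baseline to Week 16. Per patient, in units of the outcome variance:
- Treatment free at baseline: the estimate is a raw change-score contrast, with variance 2(1−r).
- Treatment restricted to post-baseline visits: the baseline is adjusted for, with variance 1−r².
- Ratio: 2(1−r)/(1−r²) = 2/(1+r).

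| r | 2(1−r) | 1−r² | Variance ratio | SE ratio | Variance ratio, 15% dropout |
|---|---|---|---|---|---|
| 0.3 | 1.40 | 0.91 | 1.54 | 1.24 | 1.46 |
| 0.5 | 1.00 | 0.75 | 1.33 | 1.15 | 1.29 |
| 0.7 | 0.60 | 0.51 | 1.18 | 1.08 | 1.15 |
| 0.9 | 0.20 | 0.19 | 1.05 | 1.03 | 1.05 |

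The dropout column comes from exact generalized least squares information matrices, which also reproduce the closed form. For class coding the ratios did not change with genotype frequency.

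**Numeric genotype.** The term then frees the baseline only in part, because the arms stay equal at genotype value 0. With complete data the variance ratio is 1.18 to 1.38 at r = 0.3, 1.11 to 1.23 at 0.5, 1.06 to 1.12 at 0.7 and 1.02 to 1.04 at 0.9, depending on genotype frequencies.

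**Absolute scale.** Assume all 80 patients are genotyped and 40% are carriers, so the cells are 16, 16, 24 and 24. Then 2/16 + 2/24 = 0.2083. At r = 0.5 the standard errors are √(1.00 × 0.2083) = 0.456 unrestricted and √(0.75 × 0.2083) = 0.395 restricted, in outcome SDs. At r = 0.7 they are 0.354 and 0.326.

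**Bias or precision?** Given a chance baseline imbalance d in the contrast, the change-score estimate shifts by (1−r)d in the opposite direction. Averaged over randomization, d is zero. Its SD is √0.2083 = 0.456, so at r = 0.5 the shift has SD 0.5 × 0.456 = 0.228. Then 0.395² + 0.228² = 0.156 + 0.052 = 0.208 = 0.456². The shift accounts for exactly the extra variance already in the unrestricted standard error.

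**The case against.** The strongest reply is that nothing is broken. Protocol 10.5.2 adds terms to models that already limit treatment to post-baseline visits, and SAP 3.8.1 codes that as `post*trtrnd*visit`. Extending the coded interaction by genotype would carry the indicator along. SAP 3.8.1 itself first names the treatment-by-visit interaction and only then restricts it, so the protocol phrase may be shorthand. This stands in part. A reader might infer that the protocol explicitly models a treatment effect at baseline; it does not say so. That is the literal reading under the three-level definition of visit. But if two competent programmers could fit different models from the sentence, it needs the qualifier, and the edit is the same under either reading.

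A reader might also infer that baseline imbalance in small cells raises the chance of a false genetic predictor. The documents do not support that. Treatment is randomized within genotype, so the unrestricted contrast has expectation zero under the null and its test keeps its nominal level. Counting the imbalance as spurious signal would count the same variance twice.

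It is also fair that the substudy is optional and exploratory, and that the point has limited reach. ADCS-CGIC is collected only at Week 16 or early termination (Protocol Table 1), so it has no baseline to share. Outcomes compared by van Elteren test (Protocol 10.4.4) have no visit interaction.

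**Conclusion.** The point holds as a wording defect with a small efficiency cost. Read with the protocol's own definition of visit, the pharmacogenetic model drops the shared-baseline adjustment for the genotype-by-treatment contrast. With class-coded genotype and complete data, the variance rises by 5% to 54% and the standard error by about 3% to 24% over r = 0.9 to 0.3.

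It would be tempting to quote a single loss, such as 18% to 33%. That range is on the variance scale and needs r between 0.7 and 0.5, class coding and no dropout, none of which the documents fix. On the standard-error scale it is 8.5% to 15.5%.

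The equal-baseline argument also assumes that being genotyped does not depend on treatment. The sample is planned for baseline but may be taken later (Protocol 7.13).

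There is no bias, no inflation of type I error, and no effect on the main trial's analysis, sample size or power. The change is a free improvement, not a correction on which the trial depends.

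**What to change.** In Protocol 10.5.2, replace the three-way term with `genotype × treatment × post-baseline visit`, coded with the 0/1 post indicator of SAP 3.8.1, as SAP 3.8.4 already does for subgroups. Keep genotype and genotype × visit unrestricted, because genotype is not randomized and true baseline differences between genotypes can exist. It would help to state in the same sentence whether genotype is a class factor or a numeric score. If the substudy has its own analysis plan, which these documents do not show, use the same wording there.

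The cost is one term in the model statement. It needs no new data and loses no validity.

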10.6 Handling of Protocol Deviations

Important protocol deviations are deviations from the protocol which could potentially have a meaningful impact on either the primary efficacy or safety. The criteria for identifying important protocol deviations and the classification of important protocol deviations will be defined prior to unblinding. To the extent feasible, rules for identifying protocol deviations will be defined without review of the data and without consideration of the frequency of occurrence of such deviations. Whenever possible, criteria for identifying important protocol deviations will be implemented algorithmically to ensure consistency in the classification of important protocol deviations across all patients.

10.7 Handling of Dropouts or Missing Data

Participants who discontinue study drug or withdraw consent will be included in mITT analyses if they received at least one dose of study drug. In the absence of a substantial difference in the

rate of withdrawal, the planned repeated measures analysis should prevent bias in estimating treatment differences. If rates of withdrawal are notably higher among participants randomized to SYN120, a nonparametric analysis that assigns the worst observed outcome to participants who withdraw prior to Week 16 will be used a conservative estimate of treatment benefit. Additional sensitivity analyses may be pursued to impute missing values or otherwise construct models for unobserved outcomes.

